7.5 Randomization

Randomization will be used to avoid bias in the assignment of subjects to treatment, to increase the likelihood that known and unknown patient attributes (e.g., demographics and baseline characteristics) are evenly balanced across treatment groups, and to enhance the validity of statistical comparisons across treatment groups.

Randomization will be performed before or at Visit 1, after the results of all screening assessments are available. Each patient will be randomly assigned to one of the two possible treatment groups.

Each study site will be assigned a block of randomization numbers. The study medication will be supplied in containers with the randomization number specified on the label.

For each randomization an investigator will contact Profil, where an unblinded person who is otherwise not involved in study procedures will assign a randomization number by means of a randomization list.

7.6 Treatment Compliance

The investigator or designated study personnel will maintain a log of all study drug dispensed and returned. Drug supplies for each subject will be inventoried and accounted for throughout the trial.

Compliance will be determined by a capsule count at each study visit. If compliance is < 80 % at two consecutive visits the subject must be withdrawn.

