5.3.7 Early Discontinuation Visit

If the patient is prematurely discontinued from further study participation he/she will be invited to attend an early discontinuation visit. If the reason for discontinuation was an adverse event that is still present by the time of the early discontinuation visit, the adverse event will be followed up until it is resolved or stabilized.

The following procedures will be performed:

Questioning for Adverse events (see section 8.17)

Concomitant medication including insulin dose (see section 8.3)

Body weight (see section 8.4)

Vital signs (see section 8.5)

Physical examination (see section 8.6)

12-lead ECG (see section 8.7)

Safety laboratory (see section 8.8)

HCG (in women only) (see section 8.10)

HbA1c (see section 8.11)

Collection of all used, unused and partly used study medication (see section 7.3)

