6.5 Withdrawal Criteria

During the study, each subject may withdraw from further participation at any time and without giving reasons. However, adequate efforts should be made to determine the reasons for discontinuing. If a patient is lost to follow-up, adequate effort should be made to determine the whereabouts and medical status of that patient, and to recover the study medication.

Patients may be discontinued early for any of the following reasons:

- An adverse event too severe to allow continuation
- Gross patient non-compliance (e.g. if compliance of drug intake is less than 80% on two consecutive visits)
- A significant protocol violation as determined by the Study Committee
- Elevation of ALT or AST of more than 3 times the upper limit of normal
- Elevation of CPK more than 10 times the upper limit of normal, or presumed or assured diagnosis of a rhabdomyolysis
- Elevation of serum-creatinine more than 2 mg/dL
- Pregnancy or nursing occurring during the trial
- Intake of a HMG-CoA reductase inhibitor (other than the study medication) during the course of the study

If a patient is withdrawn from the study the patient should be invited to attend an Early Discontinuation Visit, the reasons for removal from the study and the date of last use of study medication should be recorded.

Patients discontinuing because of an adverse event must continue to maintain contact until the event resolves or is stable, and the information must be documented by the investigator.

Patients who did not receive any medication because of withdrawal prior to the administration of the first dose will not be assigned a patient number, and data obtained up to that point will not be entered in the study database.

Patients withdrawn from the study during the first nine months after the first intake of study drug will be replaced.

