7.4 Blinding

Blinded treatment will be used to reduce potential bias during data collection and evaluation of clinical endpoints.

The investigators will have code break envelops to be opened upon specific instructions by Profil's Study Coordinator or in case of life-threatening situation which is supposed to be related to the study drug or the study drug might interfere with the patient's further medical care. The study coordinator/monitors should be informed within 24 hours about the code break. Individual code breaks by an investigator will normally result in withdrawal of the subject from the trial. The date, time, and reason for the unblinding must be documented on the appropriate page of the CRF and in the source document.

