8.11 HbA1c and Fasting C-peptide

Samples for HbA1c will be obtained at Screening Visit and at Visits 1, 3, 4 and 5. Fasting C-peptide samples will be obtained during mixed meal tolerance tests at Visits 1, 4 and 5.

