8.16 Two Hour Mixed Meal Tolerance Test

A mixed-meal tolerance test will be performed at Visit 1, Visit 4 and Visit 5. Patients will refrain from alcohol intake and unaccustomed strenuous physical activity for 48 hours prior to the test.

Prior to the test a capillary blood glucose measurement will be done and the test will only be performed, if fasting blood glucose is ≥ 4 mmol/l (72 mg/dl) and ≤ 11.1 mmol/l (200 mg/dl). If the fasting blood glucose is outside of this range, the test may be rescheduled once within the time window for this visit.

The test will be performed in the morning between 7 and 10 a.m.. The patient should take no short-acting insulin at least 6 hours prior to the test. Patients on continuous subcutaneous insulin infusion therapy should continue with the normal basal rate, but add no boluses at least 6 hours prior to the test. Patient will be fasted and will have had no food or drink (with the exception of water) and no smoking since 10 p.m. the preceding day. An I.V. line will be applied (EMLA cream may be used). Two blood samples will be drawn 5 min. and immediately before the liquid meal is taken (formal "time zero"). The patient will drink the standardized liquid meal: Boost HP (High Protein)® (Meade Johnson) in a dose of 6 ml per kg body weight with a maximum of 360 ml. The test meal should be ingested within 5 minutes. A blood sample will be drawn 90 min after the end of the ingestion of BoostHP®. (Please note that time runs from the completion of ingestion). After the test will be completed, the patients may eat and get insulin as prescribed by the investigator.

Serum glucose and C-peptide (RIA) will be analyzed in a central laboratory. The following parameter will be calculated for efficacy analysis:

Total area under the C-peptide curve, incremental area under the C-peptide curve after test meal.

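### Mandatory withdrawal from the study for poor compliance (section 7.6) ends C-peptide follow-up and removes randomised patients from the primary comparison

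*Protocol*

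**What the plan says.** Protocol section 7.6 makes withdrawal compulsory: "If compliance is < 80 % at two consecutive visits the subject must be withdrawn". Section 6.5 lists the same trigger, "Gross patient non-compliance (e.g. if compliance of drug intake is less than 80% on two consecutive visits", but under a permissive lead-in: "Patients may be discontinued early for any of the following reasons". For unblinding by an investigator, section 7.4 is also softer: "Individual code breaks by an investigator will normally result in withdrawal of the subject from the trial".

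Section 7.6 does not itself say what the patient is withdrawn from. Section 6.5 speaks of withdrawal from the study, and section 5.3.7 reads: "If the patient is prematurely discontinued from further study participation he/she will be invited to attend an early discontinuation visit". The protocol describes no status of being off drug but still followed.

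On the primary measurement, section 8.16 says "A mixed-meal tolerance test will be performed at Visit 1, Visit 4 and Visit 5", and section 8.11 says "Fasting C-peptide samples will be obtained during mixed meal tolerance tests at Visits 1, 4 and 5". The procedures listed for the early discontinuation visit in 5.3.7 include HbA1c and safety assessments, but no MMTT and no C-peptide.

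Section 6.5 adds: "Patients withdrawn from the study during the first nine months after the first intake of study drug will be replaced". Section 9.4 restricts the efficacy analysis to patients who complete the study. The one exception is an early stop at the interim analysis, when 12-month completers are used. (Section 9.4 calls that visit Visit 5; the 12-month visit is Visit 4.)

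**The concern.** Compliance is observed after randomisation, and treatment may affect it. The protocol itself expects side effects such as myalgia on active drug. If poor compliance differs between the arms in frequency, or in how it relates to C-peptide, a completers-only comparison contrasts selected patients and no longer the groups as randomised.

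Any withdrawal under this protocol ends C-peptide follow-up, so that consequence is not special to section 7.6. What 7.6 adds is a compulsory trigger for which the protocol gives no safety reason. It applies to patients who may be quite willing to keep attending, so the protocol itself causes a loss of data that could be avoided. MMTTs that are never performed cannot be supplied later by an analysis plan.

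**Working it through.** **When the rule can act.** Tablets are counted at Visits 2, 3, 4 and 5 (months 3, 6, 12 and 18). MMTTs fall at months 0, 12 and 18.

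| Two failed counts | Withdrawn at | Replaced (limit: 9 months)? | MMTTs obtained | In the efficacy analysis? |
|---|---|---|---|---|
| Visits 2 and 3 | month 6 | yes (6 < 9) | 1 of 3 (baseline) | no |
| Visits 3 and 4 | month 12 | no (12 > 9) | up to 2 of 3 (0 and 12 months) | no, as a non-completer |
| Visits 4 and 5 | month 18 | no | all 3 can be done | set aside: the last MMTT is due at that visit |

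**The plan's own figure, for scale.** Section 9.1 gives a mean of 0.37 and an SD of 0.053 nmol/l, 80 patients per group and a 20% difference.

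- Difference: 0.20 × 0.37 = 0.074 nmol/l, or 0.074/0.053 = 1.40 SD.
- Standard error: 0.053 × √(2/80) = 0.00838 nmol/l.
- Ratio: 0.074/0.00838 = 8.83, so the statement that such a difference gives p < 0.01 is true. It does not bear on the present point except to set the scale.

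**Bias from removing patients.** Let p be the share of an arm removed by the rule, and g the mean of retained minus removed patients, in SD of C-peptide. If the full-arm mean is m, then m = (1 − p)·R + p·(R − g), where R is the completer mean. Hence R = m + p·g. With no true effect, the difference between arms shifts by

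p_A·g_A − p_P·g_P.

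With 80 completers per arm, the standard error is √(2/80) = 0.158 SD. The protocol states neither p nor g, so every row below is an assumption. The two-sided 5% level is also assumed; the only level in the protocol is the 0.01 in section 9.1.

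| Removed, active vs placebo | Gap g | Shift (SD) | Shift in standard errors | Actual two-sided error |
|---|---|---|---|---|
| equal | equal | 0 | 0 | 5.0% |
| 10% vs 5% | 0.25 in both | 0.05 × 0.25 = 0.0125 | 0.08 | 5.1% |
| 10% vs 10% | 0.5 vs 0 | 0.10 × 0.5 = 0.05 | 0.32 | 6.2% |
| 20% vs 5% | 0.5 in both | 0.15 × 0.5 = 0.075 | 0.47 | 7.6% |

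The error is 1 − Φ(1.96 − s) + Φ(−1.96 − s), where s is the shift in standard errors. The third row shows that equal removal rates are not enough to remove the bias if the removed patients differ in kind between arms.

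A harsher case takes 15% vs 5% removed, a gap of 1 SD, and 68 and 76 patients remaining out of 80. The shift is 0.10 SD, the standard error √(1/68 + 1/76) = 0.167 SD, the ratio 0.60, and the error 9.2%.

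**The case against.** The strongest objection is that section 7.6 is the wrong place to look. The harm comes from the completers-only rule in 9.4 and from having no MMTT after any discontinuation. Softening 7.6 alone would leave the same problem for withdrawals due to adverse events, laboratory limits, code breaks or patient choice. That is right, and it is why the fix must reach 9.4 as well. Even so, 7.6 is the one trigger worded as compulsory, and it acts on patients who could otherwise be followed.

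The contrast between *must* in 7.6 and *may* in 6.5 carries little weight. The 6.5 list also covers pregnancy and rhabdomyolysis, so its *may* is probably loose drafting. The two sections should be aligned, but that is minor.

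The size is assumed, and most of the values are small. Against the planned effect of 1.40 SD, shifts of 0.0125 to 0.075 SD are about 1% to 5%. The 40 mg run-in, the muscle questions before the dose increase and the permitted reduction to 40 mg/day all make large tolerability-driven imbalance less likely. This stands, and it limits how strongly the point can be put.

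A later analysis plan could also bring back a 12-month MMTT already done in a patient withdrawn at month 12. That is true for that test, but not for any MMTT due after withdrawal.

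Finally, removing persistent non-takers could be defended as aiming at the effect of the drug when taken. Excluding them after randomisation does not give a randomised comparison of that effect. A completer or complier analysis can be kept as supportive.

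**Conclusion.** The concern holds. Followed as written, the protocol drops randomised patients from the primary comparison because of their compliance after randomisation, and it does not collect their later primary-endpoint data: two of three MMTTs for a withdrawal at month 6, one of three at month 12. That conclusion rests on reading 7.6 together with 5.3.7, 6.5, 8.11, 8.16 and 9.4, because 7.6 alone does not say that the patient leaves the study; no other kind of withdrawal is described.

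The direction and size of any bias cannot be derived from the protocol. If poor compliance is equally frequent in both arms and equally related to C-peptide, this route gives none. Over the assumed values it reaches 0.075 SD and an error of 7.6%, or 0.10 SD and 9.2% in the harsher case. This is an avoidable weakness that should be corrected, not one shown to overturn the result.

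**What to change.** - **Sections 6.5 and 7.6:** state one rule in both places. Compliance below 80% at two consecutive visits may end study drug, but it does not end study participation. These patients keep their scheduled 12- and 18-month MMTTs and are not replaced.
- **Section 9.4:** analyse efficacy as randomised, using all available MMTTs, with completers as a sensitivity analysis.
- **Clarification in 7.6:** say that compliance is counted against the prescribed dose. A patient reduced to 40 mg/day takes one of two tablets, which is 50% if counted against 80 mg; a permitted dose reduction should not trigger the rule.

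The text change is a wording amendment. The running cost depends on a rate that the protocol does not give. If 5% to 20% of 160 patients meet the rule, that is 160 × 0.05 = 8 to 160 × 0.20 = 32 patients. At one or two further MMTTs each, this makes 8 to 64 tests, all at visits already scheduled.

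Keeping these patients may dilute the effect. If they gain no benefit at all, the 20% difference in section 9.1 becomes 20% × 0.95 = 19% to 20% × 0.80 = 16%. On that section's own figures, 16% is 0.16 × 0.37 = 0.0592 nmol/l, still about 7 standard errors (0.0592/0.00838).

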8 STUDY ASSESSMENTS

8.1 Demographic Data

The following information will be obtained and documented at Screening visit:

- Date of birth
- Gender
- Family history of diabetes for first degree relatives
- Smoking History
- Ethnic Origin

8.2 Medical History, including Concomitant Illnesses

All relevant medical conditions and illnesses in the past and concomitant illnesses and conditions present at study entry will be documented at Screening Visit, including the date of diagnosis of type 1 diabetes and the presence or absence of ketoacidosis.

8.3 Concomitant Medication, including insulin requirements

Details on Concomitant Medication will be obtained at Screening Visit and all subsequent visits, including start date and stop date, frequency, and route of application.

Insulin treatment should be continued throughout the study with a recommended treatment goal of HbA1c below 6.5% from Visit 2 on.

However, missing this treatment goal will not be a reason for discontinuing a patient from further participation.

It is of uttermost importance, that the start date of insulin therapy is obtained and the current insulin dose is thoroughly documented at each visit.

The current insulin dose (the daily dose of all sorts of insulin) will be summed up and the weight-corrected insulin requirements will be calculated (expressed as IU per kg).

8.4 Body weight, Height and BMI

Height, without shoes (m) will be measured at Visit 1.

Weight, without shoes and overcoat (kg) will be recorded at Visit 1 and all subsequent visits.

Body Mass Index will be calculated based on Body weight and height (kg/m²).

8.5 Vital Signs

Heart rate (beats per minute), diastolic and systolic blood pressure (mmHg), in a supine position after5 minutes rest, will be measured at Screening Visit and all subsequent visits.

8.6 Physical Examination

A complete physical examination will be performed by an investigator at Screening Visit, , Visit 5 and, if applicable, Early Discontinuation Visit. Any abnormality will be recorded and described at Screening Visit and any significant changes will be recorded at subsequent visits.

8.7 12-Lead ECG

A standard 12-lead ECG will be recorded at Screening Visit, Visit 5 and, if applicable, Early Discontinuation Visit. Any abnormality will be recorded and described at Screening visit and any significant changes will be recorded at subsequent visits.

8.8 Safety Laboratory

8.8.1 Hematology

The following parameters will be determined at Screening Visit, Visits 1 to 5 and, if applicable, Early Discontinuation Visit:

Leukocytes, erythrocytes, hemoglobin, hematocrit, MCV, MCH, MCHC, platelets. Differential blood cell count will be determined at Screening Visit and Visit 5 (or Early Discontinuation Visit)

8.8.2 Clinical chemistry

The following parameters will be determined at Screening Visit and all subsequent Visits:

AST, ALT, CPK, creatinine, sodium, potassium, calcium, chloride, total protein, GGT, AP, LDH.

8.8.3 Urinalysis

A urine sample will be obtained at Screening Visit. The urinalysis will comprise the following parameters:

Blood, pH, protein, glucose, ketones, sediment.

8.8.4 Coaquiation

A blood sample for coagulation parameters (PTT and INR) will be obtained at Screening Visit.

8.9 Serum Lipids

Serum Lipids will be tested at Screening Visit, Visits 1 to 5 and , if applicable, at Early Discontinuation Visit.

Serum samples will be obtained after fasting for at least 10 hours. The following parameters will be tested:

Total cholesterol, HDL-cholesterol, LDL-cholesterol, and triglyerides.

The tests will be performed in a central laboratory for all study sites.

From Visit 1 to 5 the investigators will be blinded for the results of the serum lipid measurements to ensure that no conclusions on the treatment group can be drawn.

8.10 Pregnancy Test

In women, a pregnancy test will be performed at screening and all subsequent visits and at any time during the study, when a pregnancy is assumed.

8.11 HbA1c and Fasting C-peptide

Samples for HbA1c will be obtained at Screening Visit and at Visits 1, 3, 4 and 5. Fasting C-peptide samples will be obtained during mixed meal tolerance tests at Visits 1, 4 and 5.

8.12 Beta-cell Autoantibodies

The following Autoantibodies will be determined at Screening Visit and at Visits 3, 4, and 5:

- GAD65
- IA2
- ICA

8.13 Plasma CRP

Plasma-CRP will be tested at Visits 1, 2, 4 and 5.

8.14 Serum Cytokines and Serum Chemokines

Blood samples for assays on immune mediators will be performed at Visits 1, 2, 4 and 5. Tests will be done for acute phase proteins (CRP, Fibrinogen), soluble adhesion molecule (sICAM-1), cytokines (IL-4, IL-5, IL-6, IL-10, IL-12, IL-13, IL-18 and IFN-gamma) and chemokines (MIP-1 alpha, MCP-1, IP-10, Eotaxin, MIP-2). This selection of parameters may be fractionally changed, if needed. An additional 1ml serum and 0.5 ml plasma will be collected at these visits for

An additional 1ml serum and 0.5 ml plasma will be collected at these visits for possible additional markers on protein or transcriptional level.

8.15 Transcriptional Analysis

At Visits 1 and 2, Serum and Plasma in a subset of 50 patients will be sampled for analyses of expression of immune mediators on transcriptional level. A laboratory manual of the procedures and details of the tests will be provided prior to the start of the study.

8.16 Two Hour Mixed Meal Tolerance Test

A mixed-meal tolerance test will be performed at Visit 1, Visit 4 and Visit 5. Patients will refrain from alcohol intake and unaccustomed strenuous physical activity for 48 hours prior to the test.

Prior to the test a capillary blood glucose measurement will be done and the test will only be performed, if fasting blood glucose is ≥ 4 mmol/l (72 mg/dl) and ≤ 11.1 mmol/l (200 mg/dl). If the fasting blood glucose is outside of this range, the test may be rescheduled once within the time window for this visit.

The test will be performed in the morning between 7 and 10 a.m.. The patient should take no short-acting insulin at least 6 hours prior to the test. Patients on continuous subcutaneous insulin infusion therapy should continue with the normal basal rate, but add no boluses at least 6 hours prior to the test. Patient will be fasted and will have had no food or drink (with the exception of water) and no smoking since 10 p.m. the preceding day. An I.V. line will be applied (EMLA cream may be used). Two blood samples will be drawn 5 min. and immediately before the liquid meal is taken (formal "time zero"). The patient will drink the standardized liquid meal: Boost HP (High Protein)® (Meade Johnson) in a dose of 6 ml per kg body weight with a maximum of 360 ml. The test meal should be ingested within 5 minutes. A blood sample will be drawn 90 min after the end of the ingestion of BoostHP®. (Please note that time runs from the completion of ingestion). After the test will be completed, the patients may eat and get insulin as prescribed by the investigator.

Serum glucose and C-peptide (RIA) will be analyzed in a central laboratory. The following parameter will be calculated for efficacy analysis:

Total area under the C-peptide curve, incremental area under the C-peptide curve after test meal.

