 To assess the effect on systemic immune abnormalities in patients with type 1 diabetes mellitus as measured by effects on beta-cell autoantibodies, blood cytokines and chemokines on protein and transcriptional level

Number of patients: Up to 160 patients with recent onset type 1 diabetes

mellitus should complete all study procedures. Patients who are withdrawn from the study during the first nine

months of treatment will be replaced.

Number of study sites: About 20 study sites will participate in this trial. The

number of sites may be adjusted to assure a sufficient

number of patients can be included.

The German Diabetes Clinic will participate with

approximately 25 to 35 patients.

DIATOR

Protocol Version 2.3 07/01/2004

Efficacy endpoints:

Primary efficacy endpoint:

 Area under the C-peptide curve in a 2 hour mixed meal tolerance test after 12 months and 18 months of treatment

Secondary efficacy endpoint:

HbA1c and insulin requirements after 12 and 18 months of treatment

Study drug regimen:

starting dose 40 mg/day for 4 weeks, then increase to 80 mg/day, in case of side effects reduction to 40 mg/day

Frequency: daily, as recommended

Route: oral

Duration: 18 months

Table of contents

1	LIST	of Addreviations	8
2	lovo	estigators and Study Administrative Structure	10
_	2.1	Requirements of the Investigator(s) and Study Sites	
	2.2	Administrative Structure	10
	۷.۲	Administrative offactore	
3	Intro	oduction	12
_			
4	Stuc	dy Objectives	14
5		rall Study Design and Procedures	
	5.1	Study Design	
	5.2	Study Flow Chart	
	5.3	Study Procedures	
	5.3.		
	5.3.		
	5.3.		
	5.3.4		
	5.3.		
	5.3.0 5.3.1		
	5.5.	7 Early Discontinuation Visit	21
6	Sele	ection of Study Population	22
_	6.1	Primary Diagnosis	
	6.2	Number of Subjects	
	6.3	Inclusion Criteria	
	6.4	Exclusion Criteria	
	6.5	Withdrawal Criteria	23
7		atments to be Administered	
	7.1	Identity of Investigational Product	
	7.2	Labeling and Packaging of the Investigational Product	
	7.3	Drug Accountability	
	7.4	Blinding	
	7.5	Randomization	
	7.6	Treatment Compliance	20
8	Stuc	dy Assessments	27
_	8.1	Demographic Data	
	8.2	Medical History, including Concomitant Illnesses	
	8.3	Concomitant Medication, including insulin requirements	
	8.4	Body weight, Height and BMI	
	8.5	Vital Signs	
	8.6	Physical Examination	28
	8.7	12-Lead ECG	
	8.8	Safety Laboratory	
	8.8.	0,	
	8.8.	2 Clinical chemistry	28

8.	.8.3	Urinalysis	
8.	.8.4	Coagulation	
8.9		rum Lipids	
8.10		gnancy Test	

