5 OVERALL STUDY DESIGN AND PROCEDURES

5.1 Study Design

This study will be conducted as a randomized, double-blind, placebo-controlled, outpatient, parallel group study in adult patients with recent onset type 1 diabetes. Patients will be randomly assigned to treatment with either atorvastatin or placebo in a one-to-one manner. The treatment phase will be 18 months for each patient. Patients who are withdrawn from the study during the first nine months of the treatment phase will be replaced. A maximum of 160 patients will complete all study procedures. The number of subjects included may be adjusted following an interim analysis as specified in section 9.9)

Starting dose will be 40 mg per day of atorvastatin or a matching number of placebo tablets. After a run-in period of 4 weeks the daily dose will be increased to 80 mg per day or matching placebo. In case of side effects (e.g. myalgia) the dose will be reduced to 40 mg per day by the discretion of the investigator.

Efficacy on beta-cell preservation will be assessed by means of two-hour mixed-meal tolerance tests at baseline and after 12 months and 18 months of treatment. Safety data and data on metabolic control will be obtained at baseline and after 3, 6, 12 and 18 months of treatment.

Patients should continue insulin treatment throughout the study. A tight glycemic control should be aimed (Target HbA1c ≤ 6.5 %) from Visit 2 on.

5.2 **Study Flow Chart**

Visit	Screening	Visit 1 *	Visit 2	Visit 3	Visit 4	Visit 5	Early Discontinuation
Time	-28 to -2 days	0	3 months (±2 weeks)	6 months (± 10 days)	12 months (± 2 weeks)	18 months (± 2 weeks)	
Informed consent	х						
Inclusion/Exclusion Criteria	х						
Randomization		X					
Demographic Data	х						
Medical History and concomitant Illnesses	х						
2 h MMTT		X			х	х	
12 lead ECG	х					х	х
Vital signs	х	X	х	x	x	х	х
Body height ¹ , weight and BMI		х	х	х	х	х	х
Physical examination	х					х	x
Adverse Events		х	х	X	х	х	х
Concomitant Medication	х	х	х	х	х	х	х
Documentation of Insulin dose	Х	Х	х	х	х	х	х
Drug accountability		X	х	x	x	х	x
Hematology	х	х	х	х	х	х	х
Clinical Chemistry ¹	х	х	х	х	х	х	х
Serum Lipids	х	х	х	х	х	х	х
Coagulation	Х						
Urinalysis	х						
Transcriptional studies		х	х				
Cytokines/chemokines		Х	х		х	х	
Beta cell autoantibodies	х			х	х	х	
HCG ²	х	Х	х	х	х	х	х
Plasma CRP		х	х		х	х	
HbA1c	х	х		х	х	х	х
Fasting C-peptide		X³			X ³	X³	

Visit 1 only ²only female patients ³ sampled during mixed meal tolerance test

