9.8 Evaluation of Clinical Efficacy

Patients will be included in the evaluation of clinical efficacy as outlined in section 9.4. If appropriate, the results may be stratified for time from diagnosis to visit 1, gender, age, status of autoimmune antibodies and C-peptide levels at the entry into the study.

The concentration-time courses of basal C-peptide secretion will be summarized separated by treatment. Standard parameters of descriptive statistics will be calculated for each of the sampling points and for the area under the C-peptide concentration curves. Means at any time will only be calculated, if at least 2/3 of the individual data were measured and were above the limit of quantification (LOQ). For the calculation of the mean value a data point below LOQ will be substituted by half of this limit. Where values below LOQ are included in the calculation of mean values, these means will be marked in the relevant summary table.

C-peptide values will be compared for the two treatment groups using standard statistical tests that will be specified in a statistical plan that will be amended. Area under the C-peptide curve of the MMTT will be analyzed as mentioned above. Other efficacy parameters like C-peptide at different sampling times, maximum C-peptide concentration or incremental area under the C-peptide curve may be calculated where appropriate.

Statistical analyses of weight corrected Insulin-doses, HbA1c, Serum-lipids and Serum-CRP levels will be done accordingly.

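### The Synopsis makes C-peptide AUC in a 2-hour meal test primary, but the sampling in 8.16 and the sizing in 9.1 fit only a stimulated concentration

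*Protocol*

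**What the plan says.** **Endpoint.** The Synopsis lists one primary efficacy endpoint: "Area under the C-peptide curve in a 2 hour mixed meal tolerance test after 12 months and 18 months of treatment". Section 5.1 gives the test the same duration: "Efficacy on beta-cell preservation will be assessed by means of two-hour mixed-meal tolerance tests at baseline" and again at 12 and 18 months. Section 8.16 carries the two-hour label in its title.

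**Sampling.** Section 8.16 first takes fasting blood: "Two blood samples will be drawn 5 min. and immediately before the liquid meal is taken". It then takes one stimulated sample: "A blood sample will be drawn 90 min after the end of the ingestion of" the liquid meal. It adds: "Please note that time runs from the completion of ingestion". The flow chart in 5.2 and the visit lists in 5.3 add no sampling time; the visit lists refer back to 8.16.

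**Derived parameters.** Section 8.16 names these for the efficacy analysis: "Total area under the C-peptide curve, incremental area under the C-peptide curve after test meal". Section 9.8 plans descriptive statistics at each sampling point and for the AUC, and allows, where appropriate, "C-peptide at different sampling times, maximum C-peptide concentration or incremental area under the C-peptide curve".

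**Other descriptions of the main variable.** The last paragraph of the Introduction says preservation of beta-cell function is judged by stimulated C-peptide levels. Objective 1 in section 4 refers to C-peptide after a liquid mixed meal. Section 9.1, explicitly for the primary endpoint, uses stimulated C-peptide of 0.37 ± 0.053 nmol/l (mean ± SD) and a 20% difference with 80 patients per group.

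**The concern.** An area under a curve needs enough points to trace the curve and a last point at the end of the interval. Section 8.16 provides one point after the meal, 30 minutes short of the two hours in the test's name. The protocol's sizing, introduction and first objective meanwhile speak of a stimulated level, which is a different variable with different units.

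The efficacy conclusion rests on the primary variable. So do the possible sample size adjustment and early stopping at the interim analysis (9.9, 13.4). If the texts are not reconciled, the choice between a two-point AUC, an extrapolated two-hour AUC and the 90-minute value stays open, possibly until data have been seen. If the AUC was meant, sites that follow 8.16 exactly will fail to collect the needed samples in every patient at Visits 1, 4 and 5. Those samples cannot be recovered later.

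**Working it through.** **Inputs.** Sampling at −5, 0 and 90 min, with the meal drunk within 5 min (8.16). Test length 120 min (Synopsis, 5.1, title of 8.16). Mean 0.37 nmol/l, SD 0.053 nmol/l, 20% difference, 80 per group (9.1).

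**1. The plan's own figure.** Section 9.1 states that a 20% difference would be significant at p < 0.01.
- Difference = 0.20 × 0.37 = 0.074 nmol/l.
- Standard error = 0.053 × √(2/80) = 0.00838.
- t = 0.074 / 0.00838 = 8.83; two-sided p is about 2 × 10⁻¹⁵.

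The statement is true as an inequality. What matters here is that every input is a concentration; no mean or SD of an AUC appears.

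**2. AUC from the scheduled samples.** With C0 the fasting value and C90 the 90-minute value:
- Total AUC(0–90) = 90 × (C0 + C90)/2 = 45 × (C0 + C90).
- Incremental AUC(0–90) = 45 × (C0 + C90) − 90 × C0 = 45 × (C90 − C0).
- Coverage = 90/120 = 75%, leaving 30/120 = 25% unobserved.
- If time is counted from the formal zero before the meal, the sample can fall at 95 min, and coverage is 95/120 = 79%. Section 8.16 gives both a time zero before the meal and a clock that starts at the end of ingestion, so the interval is uncertain by up to 5 min.

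**3. Extending to 120 min.** Carrying C90 forward gives 45 × (C0 + C90) + 30 × C90 = 45 × C0 + 75 × C90. This is still a fixed combination of the same two values. Only the fasting weight changes, from 45/90 = 50% to 45/120 = 37.5%. An integration rule can choose weights; it cannot add information.

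**4. What the two points cannot see.** This is an illustration with assumed curves on a 0, 15, 30, 60, 90, 120 min grid, all with C0 = 0.20 and C90 = 0.37 nmol/l. The protocol gives no curve and no fasting value.

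| Assumed shape (nmol/l) | Two-point AUC(0–90) | Carried forward to 120 | Full-grid AUC(0–120) | Full-grid incremental |
|---|---|---|---|---|
| Steady rise, then fall (0.20, 0.23, 0.26, 0.31, 0.37, 0.33) | 25.65 | 36.75 | 36.15 | 12.15 |
| Early peak (0.20, 0.30, 0.42, 0.45, 0.37, 0.30) | 25.65 | 36.75 | 44.55 | 20.55 |
| Late peak (0.20, 0.21, 0.23, 0.30, 0.37, 0.42) | 25.65 | 36.75 | 36.23 | 12.23 |

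Units are nmol/l × min. The two-point incremental AUC is 45 × (0.37 − 0.20) = 7.65 in every row. Patients whose two-hour areas differ by 44.55 − 36.15 = 8.40 receive the same value.

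**5. Effect size on the two scales.** On the same assumed C0 = 0.20, a 20% difference in C90 alone is 0.074/(0.20 + 0.37) = 13% of the two-point AUC. It is 20% only if the fasting value moves in proportion. The difference in 9.1 therefore does not carry over to the AUC without a further assumption.

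**The case against.** The strongest reply is that an AUC can be computed. The Synopsis attaches the two hours to the test and states no integration limits, so a 0–90 minute trapezoid could be declared the AUC, and the limits and rule may properly be left to the announced statistical plan. That stands as far as it goes: a crude 0–90 minute area is available. A statistical plan cannot, however, supply samples that the protocol does not schedule, and the available area does not span the test that the endpoint names.

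Second, the 90-minute sample serves the Introduction, objective 1 and section 9.1 well. This also stands. A reader might infer that the primary variable cannot be derived at all, or that the trial cannot answer its question. The documents do not support that: stimulated C-peptide is obtainable. The fault is that two variables compete for the primary role.

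Third, a reader might take 8.16 and 9.8 as also making the AUC primary. Only the Synopsis does so. Section 8.16 lists total and incremental AUC without ranking them, and the maximum concentration and similar items in 9.8 are optional. They show that the text presumes a sampled curve, but they are not commitments the plan fails to meet.

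Fourth, both arms are sampled alike, so the mismatch does not by itself bias the comparison. That stands too. The areas from 36.15 to 44.55 rest on assumed curves and show what is unobserved, not an error in the treatment effect.

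**Conclusion.** Wrong as written, and to be settled before enrolment. The primary variable is named inconsistently: an AUC in a two-hour test in the Synopsis, a stimulated concentration in the Introduction and 9.1. The sampling in 8.16 supports only the second.

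Taken as an AUC, the endpoint reduces to 45 × (C0 + C90). That is a rescaled mean of a fasting and a 90-minute value, with no data in the last 25% of a 120-minute test and none between 0 and 90 minutes. This applies to every patient at all three meal tests. The 25% assumes that the AUC was meant to span the two hours in the test's name; it is about 21% if the sample falls 95 minutes after time zero. The algebra needs no assumption about curve shape.

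No bias, loss of power or false-positive risk is claimed. The documents give no AUC mean or SD from which to work one out.

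**What to change.** Reconcile the Synopsis and sections 5.1, 8.16, 9.1 and 9.8 by one amendment before enrolment. Either route resolves the conflict.

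- **(a) Concentration as primary.** Name the C-peptide concentration 90 minutes after the end of ingestion as the primary endpoint, matching 8.16 and the type of variable in 9.1. Label any two-point AUC as 0–90 min and make it secondary. No extra blood is needed, but this changes the primary endpoint and needs Study Committee agreement and ethics approval under 13.1. The Introduction says the endpoint follows a cited guideline, so the sponsor should check the change against it.
- **(b) AUC as primary.** Schedule further post-meal samples through 120 minutes from the I.V. line already placed. State one time origin and the trapezoid rule. The cost is a few extra samples and assays per test: each added time point means up to 160 × 3 = 480 samples among completers. The visit grows by about 30 minutes only if the test is now meant to end at the 90-minute draw. This also needs an amendment.

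In either case, rewrite the sample size statement in 9.1 for the variable chosen. Under (b) that requires a mean and SD for the AUC.
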